5.6 Data Analysis

Quantitative Statistical Analysis (Aims 1 and 2): Differences in hand hygiene adherence and duration between intervention and control groups will be assessed using Fisher's exact test and t-test, as appropriate. Risk differences in adherence to duration of hand hygiene will be calculated for both intervention and control groups. Because the primary outcomes for Aim 1 (i.e., hand hygiene adherence and duration) are expected to occur frequently, we will use generalized linear models to evaluate differences in hand hygiene adherence and duration for the intervention versus control group, with the Poisson distribution (log link) and robust error variance. Models will account for provider type and level, and will incorporate clustering by physician team (and separately for nursing unit). Statistical significance will be calculated for the intervention (intervention vs. control) coefficient.

As a secondary outcome for Aim 1, we will assess changes and differences in hand hygiene perception based on response to select questions from PSHW. For Aim 2, mindfulness will be based on responses to FFMQ and well-being will be based on responses to WBI. FFMQ and WBI scales will be scored according to the published algorithms. Descriptive statistics will be used to summarize participant scores from pre- and post-intervention, as well as 6-month post-intervention follow-up assessments. Within-group paired-samples t-tests will be used to test for improvement in participant scores across the baseline, post-intervention (~14 days for physicians and 1-month for nurses), and 6-month post-intervention follow-up periods, for the intervention and control groups separately. Analyses will use list-wise deletion for missing data. Participants not completing all surveys will still be included in any analysis for which they provide data. For all analyses, p values less than 0.05 will be considered significant and all tests will be two-tailed. Analysis of covariance (ANCOVA) models will then be used to assess relative changes in mindfulness, well-being, and hand hygiene perceptions across groups, the most direct test of discriminant validity. In these models, post-test scores will be predicted by group status controlling for pre-test scores.

Power - Based on a range of 10%-15% significant percent change in hand hygiene adherence from our pilot data,⁷² we are anticipating an expected increase in hand hygiene adherence due to the intervention from approximately 80% at baseline to 88%-92% at follow-up. We will have 79.8% power to detect this 10% increase based on a fixed total sample size of 334 with a two-sided alpha of 0.05, assuming an average of 60 observed hand hygiene opportunities per provider per measurement time point (i.e., intervention and follow-up), and taking into account clustering of data within site/team/unit (assumed Intraclass Correlation Coefficient=0.4).⁸² For assessing differences in the select PSHW questions we will have 70.1% power to detect an effect size of 0.15.⁸³ For assessing differences in FFMQ and WBI scores, we will have >95% power to detect effect sizes ranging from 0.3 to 0.75 as found in prior studies.^{65,84,85}

Qualitative Phase (Aim 3): In Aim 3, we will begin the process of identifying the facilitators and challenges of incorporating mindfulness into clinical practice and developing a deeper understanding of perceptions and experiences related to using mindfulness in the clinical setting. We will employ a case-study methodology, conducting semi-structured interviews. First, we will conduct interviews with intervention participants (attending physicians, senior residents, interns, and nurses) at each site. We will ask participants about their experience with mindfulness and opinions about using it as a possible tool to promote hand hygiene, infection prevention, and provider well-being. Interviews will occur at the conclusion of selected intervention phase observation periods. We will invite members of the intervention arms to discuss their experience of attempting mindful hand hygiene, the concept of mindfulness for healthcare providers in the inpatient setting, the hand hygiene-based mindfulness intervention components (i.e., online modules, mindfulness app, group-facilitated discussions, mindful hand hygiene moments), challenges to performing mindfulness, and the potential benefits for providers and patients. Based on the literature and our prior experience, data saturation is generally achieved after interviewing 10-12 individuals at a site. We plan to interview approximately 8 physician team members and 4-6 nurses at each site. Interviews will include a semi-structured interview guide (**Appendix D**) to stimulate discussion of the realities and challenges of practicing mindfulness through hand hygiene in the clinical setting. Second, qualitative data will also be collected and evaluated from each site's group-facilitated guided discussions. During these guided discussions it is expected that participants will talk about their insights on learning and their own personal experiences practicing mindfulness during the intervention. All guided discussions, along with the interviews, will be recorded, de-identified, and transcribed for analysis. These recordings will be transcribed internally by staff at the VA Ann Arbor CCMR offices. The interviews and transcripts will be stored on secure VA CCMR servers with access limited to approved project staff. Transcripts will be reviewed and data central to the aims of this study will be extracted and analyzed. We will use the 7 aspects of Mindful Practice⁸⁶ as they may relate to hand hygiene as a guide for data interpretation.

All interviews will be conducted by 2 to 3 members our team and will generally include the study Principal Investigator [name], other study co-investigators PD/PI [name], or Co-Investigators [name] and [name], non-clinician qualitative experts [name] or [name], and project support staff (the project manager or research assistant). All interviews will be audio-recorded and transcribed for analysis; field-notes and site materials will be preserved. Participants will be informed when the audio recording is in process and may request to stop the audio recording at any time.

A descriptive-content analysis will be conducted on the qualitative data from interviews and group discussions.⁸⁷ Three to four members of the study team will begin by independently reading a sample of interview and group discussion transcripts and together develop a preliminary coding scheme to help guide the analysis. A codebook will be created that includes both deductive codes, identified prior to coding based on key study categories, and inductive codes that emerge directly from the data. Two members of the study team will use this codebook, which will be revised periodically as additional codes emerge, to independently review and code all transcripts. If new codes emerge, previously coded transcripts will be re-analyzed to ensure consistency in the

application of codes. The two coders will meet regularly, and with other study team members as needed, to discuss and resolve any discrepancies in coding until agreement is reached. We will use a VA approved qualitative analysis program like MAXQDA (VERBI Software, Berlin, Germany) will be used to manage and organize the qualitative data. Once all of the data have been coded and entered into MAXQDA, members of the larger study team will identify key themes. All recordings and transcripts will be stored on a secure VA CCMR server, with access limited to approved study staff.

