Mindful Hand Hygiene to
Reduce Infections Among
Veterans While Enhancing
Provider Well-Being

NCT05261282

December 5, 2025

Data Analysis Plan

Differences in hand hygiene adherence and duration between intervention and control groups will be assessed using Fisher's exact test and t-test, as appropriate. Differences in adherence to duration of hand hygiene will be calculated for both intervention and control groups. As a secondary outcome for Aim 1, the investigators will assess changes and differences in hand hygiene perception based on responses to select questions from the PSHW. For Aim 2, mindfulness will be based on responses to the FFMQ and well-being will be based on responses to the WBI. Survey scales will be scored according to the published algorithms. Descriptive statistics will be used to summarize participant scores from baseline and post-intervention, as well as 6-month post-intervention (sustainability) follow-up assessments. Within-group paired-samples t-tests will be used to test for improvement in participant scores across the baseline, post-intervention (~14 days for physicians and 1-month for nurses), and 6-month post-intervention (sustainability) follow-up periods, for the intervention and control groups separately. Participants not completing all surveys will still be included in any analysis for which they provide data. Listwise deletion for observations containing less than 85% complete responses for the FFMQ or WBI items will be used. Missing values for observations with at least 85% responses for the FFMQ or WBI items will be imputed using the average value obtained from non-missing values within each respective subscale. Multilevel linear mixed regression models will be used to assess changes in mindfulness and well-being across groups and the effectiveness of the intervention. Mixed models account for correlation between repeat measurements on the same participant and accommodate missing data across time points. Random effects will be modeled to account for clustering of survey responses at the clinician level. All models will be adjusted for fixed effects for clinician role (physician/nurse) and intervention fidelity. For all analyses, p-values less than 0.05 will be considered significant and all tests will be two-tailed.

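### Aim 1 has two unranked primary outcomes, each judged at two-sided 0.05; if either can carry the claim, the false-positive chance is above 5% and up to 9.75%

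*Protocol*

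**What the plan says.** Protocol section 5.6 introduces its regression model for Aim 1 with "Because the primary outcomes for Aim 1 (i.e., hand hygiene adherence and duration) are expected to occur frequently". Two outcomes are therefore primary, with no order between them. For the models it adds: "Statistical significance will be calculated for the intervention (intervention vs. control) coefficient". The threshold is common to everything: "For all analyses, p values less than 0.05 will be considered significant and all tests will be two-tailed".

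The SAP keeps both outcomes side by side: "Differences in hand hygiene adherence and duration between intervention and control groups will be assessed using Fisher's exact test and t-test, as appropriate". It does not carry over the Poisson model. Within Aim 1 it places only perceptions lower ("As a secondary outcome for Aim 1, the investigators will assess changes and differences in hand hygiene perception") and repeats the general threshold: "For all analyses, p-values less than 0.05 will be considered significant and all tests will be two-tailed".

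The power paragraph of section 5.6 builds its main calculation on adherence: "we are anticipating an expected increase in hand hygiene adherence due to the intervention from approximately 80% at baseline to 88%-92% at follow-up", and then "We will have 79.8% power to detect this 10% increase based on a fixed total sample size of 334 with a two-sided alpha of 0.05". It also gives power for the PSHW questions (70.1%) and for FFMQ and WBI (above 95%). It gives none for duration.

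Section 3.0 of the protocol lists adherence, duration and perceptions together under Aim 1, also without ranking.

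**The concern.** With two primary outcomes, a plan has to say what counts as success: one named outcome, either, or both. This plan does not. Under a blanket 0.05 rule, a null result on adherence with p = 0.04 on duration could be presented as a positive primary finding, and nothing in either document would rule that out. The error rate behind such a claim is not the 5% that a reader would assume.

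Duration is the weaker of the two outcomes to leave in that position. It has no stated target effect. Section 5.1 also expects fewer physician data for it: 480-720 duration measurements per arm at each site, against 1,920-5,670 room-entry moments for adherence. The protocol intends wider VHA deployment if the intervention succeeds, so the meaning of success should be fixed beforehand.

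**Working it through.** **Inputs.** Two primary outcomes (protocol 5.6). Alpha 0.05, two-sided, for each test (protocol 5.6 and SAP). For adherence: stated power 79.8%, N = 334, 80% rising to 88% (the 10% increase read as relative), 60 opportunities per provider, ICC 0.4 (protocol 5.6, power paragraph). The correlation between the two test statistics is not given, so it is varied as an assumption.

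**1. The plan's own power figure.** Take 167 providers per arm and cluster by provider.
- Design effect: 1 + 59 × 0.4 = 24.6.
- Effective observations per arm: 167 × 60 / 24.6 = 407.3.
- Mean proportion 0.84. Standard error under the null: √(2 × 0.84 × 0.16 / 407.3) = 0.02569. Under the alternative: √((0.80 × 0.20 + 0.88 × 0.12) / 407.3) = 0.02554.
- Power: Φ((0.08 − 1.96 × 0.02569) / 0.02554) = Φ(1.161) = 87.7%.

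This does not reproduce 79.8%. An ICC of 0.5 (80.0%) or an unstated 20% loss of providers (79.7%) would match. That mismatch is a separate matter and does not enter the error-rate calculation below.

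**2. Chance of at least one false positive in two tests at 0.05.**
- Independent: 1 − 0.95² = 1 − 0.9025 = 9.75%, which is 1.95 times 5%.
- Upper bound whatever the dependence: 0.05 + 0.05 = 10%.
- Correlated, taking the two statistics as bivariate normal: 1 − P(|Z₁| < 1.96 and |Z₂| < 1.96).

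| Assumed correlation | At least one false positive |
|---|---|
| 0 | 9.75% |
| 0.2 | 9.6% |
| 0.5 | 9.1% |
| 0.7 | 8.4% |
| 0.8 | 7.8% |
| 0.9 | 7.0% |

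The rate falls to 5% only as the correlation approaches 1. The data-collection text in section 5.1 makes that unlikely. Duration is timed at room exit only, for all nurses and for half of the attending observations. Adherence is recorded at entry and exit and includes senior residents and interns.

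**3. What control would cost.**
- Bonferroni, 0.025 each: 1 − 0.975² = 4.94% if independent. Scaling from the stated power, the standardised effect is 0.8345 + 1.960 = 2.7945. At alpha 0.025 the power is Φ(2.7945 − 2.2414) = Φ(0.553) = 71.0%. Restoring 79.8% would need ((2.2414 + 0.8345) / 2.7945)² = 1.21 times the information.
- Fixed sequence, adherence then duration, each at 0.05: if adherence has no effect, any false claim first requires a false positive on adherence, at most 5%. If adherence has an effect and duration has none, the only possible false claim is on duration, again at most 5%. Power for adherence is unchanged.

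**The case against.** The strongest reply is that the success rule behind 9.75% is supplied by the reader. The protocol says only that significance will be computed for the intervention coefficient; no sentence says that either outcome suffices. If both were required, the joint error would not exceed 5%. This stands as a condition on the figure. It does not remove the gap, because neither document requires both, and the blanket threshold lets each be called significant on its own.

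Three stronger readings are tempting, and the documents do not support them.
- **That the error rate is simply doubled.** 9.75% is the value for independent tests. Adherence and duration come from overlapping providers and moments, and no correlation is given.
- **That only adherence was powered.** PSHW, FFMQ and WBI have power statements too. The remark holds only between the two Aim 1 primary outcomes.
- **That every scale needs correction or demotion.** PSHW is already secondary. FFMQ and WBI belong to Aim 2, a separate aim with its own power statement, and the 9.75% concerns Aim 1 alone.

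Two further objections bear on the remedy. An ordering sentence alone would not secure 5%, because the protocol tests these outcomes both by simple tests and by a clustered model, while the SAP keeps only the simple tests, which ignore clustering. That is correct, and the fix must name the test. Putting adherence first is also partly a choice: section 2.0 reports 90% adherence by direct observation at Ann Arbor, which leaves limited room to improve, and presents duration as a new element. Holm's procedure or a single named primary outcome would also control the error. Adherence first is preferred here because the protocol's own power calculation rests on it and because it costs adherence nothing.

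**Conclusion.** The point holds as a missing decision rule with a calculable consequence. If significance on either outcome is treated as primary success, the false-positive chance for Aim 1 exceeds 5% and can reach 9.75%; it is about 9.1% at correlation 0.5 and 7.0% at 0.9. This rests on three assumptions: either outcome suffices, the correlations are as tabulated, and each test holds its nominal 5%. The last would fail if the SAP's unadjusted Fisher's exact test and t-test were used on clustered observations, so the range is stated before any clustering problem.

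A reader might infer that the investigators plan to claim success on whichever outcome is significant. The documents do not say so; they only leave it open. This is a cheap improvement, not a flaw that undermines the trial.

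**What to change.** Add to the SAP:
- Adherence is tested first at two-sided 0.05. Duration is confirmatory at two-sided 0.05 only if adherence is significant; otherwise it is reported descriptively.
- For each outcome there is one confirmatory test: the cluster-adjusted intervention coefficient from the Poisson model with robust variance in protocol section 5.6. It replaces Fisher's exact test and the t-test in that role. The text should make clear which single coefficient is meant, including the time point and whether physicians and nurses share one model, and on what scale duration is analysed.
- The order is recorded before arm-level results are seen. The SAP is dated December 5, 2025; if results by arm have already been seen, that should be disclosed.

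No change is needed for PSHW, FFMQ or WBI.

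The cost is a few sentences. Adherence keeps its full alpha and power, whereas Bonferroni would take the stated 79.8% to about 71.0%. The downside is that duration cannot be claimed as confirmatory if adherence is not significant.

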5.0 Study Procedures

5.1 Study Design

Research Design: A multi-center, repeat-measures randomized controlled mixed-methods trial.

Study Population: The proposed study will focus on Internal Medicine physicians who are part of inpatient care teams and nurses providing care on medical and medical/surgical units at LTC Charles S. Kettles VAMC in Ann Arbor, MI and MEDVAMC in Houston, TX. Medical students, surgical physicians, and physicians on sub-specialty teams will not be included. At both participating facilities the inpatient care teams are predominately composed of 1 attending, 1 senior resident, 2 interns, and up to 3 medical or physician assistant students. Interns and senior residents are usually assigned to a team for 4-week blocks (occasionally 2 weeks), while attendings rotate approximately every 2 weeks. The Ann Arbor VAMC has 3 medical or medical/surgical inpatient units, while MEDVAMC has 5 units. At both facilities each nursing unit employs between 20-30 nurses. We will aim to recruit approximately 30 attendings, 72 residents and 40 nurses at Ann Arbor VAMC. As MEDVAMC is larger, with a greater number of inpatient care teams and nursing units than the Ann Arbor VAMC, we will aim to recruit approximately 40 attendings, 72 residents and 90 nurses. Our target study sample size is a total of 344 physicians and nurses (167 intervention/177 control). For Aim 3, we plan to interview approximately 8 physician team members and 4-6 nurses from the intervention arm at each site.

General Study Overview and Outcome Measures:

A summary of the proposed study activities at each participating site is presented in **Table 2** below.

Table 2: Overview of Study Activities at Each Study Site

| Study Detail | Physicians | Nurses |
|----------------------------------|--|--|
| Target | Attendings, senior residents and interns on inpatient medicine teams | Nurses on medical or medical/surgical units |
| Teams/Units Participating | 2 teams each month for 12 months randomized to intervention or control arm at each site | 2 units (1 intervention; 1 control) at Ann Arbor VAMC & 4 units (2 intervention; 2 control) at MEDVAMC randomized once & followed for 12-months |
| Estimated number of participants | 107 intervention and 107 control | 20 intervention and 20 control at Ann Arbor VAMC; 40 intervention and 50 control at MEDVAMC |
| Habituation Period | 1 month | 1 month |

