Randomization – At each study site the participating physician teams and nursing units will be randomly assigned into one of two study arms (intervention/control). For physician teams, this will occur on a rolling basis for 12 months with 2 physician teams randomly selected at each site each month for participation (1 intervention, 1 control). Once randomized, an email will be sent to the initial attending of the team introducing the study and asking them to reply to the email if they would prefer to opt out and not have their team participate in the randomized controlled trial. If the attending physician from a team refuses to allow their team to participate, the next team identified from the randomized list will be approached to participate. If a new attending joins the team mid-month, they will be approached to participate in the study, but will be automatically assigned to the same randomization group as the rest of their team.

Similarly, a total of 2 medical/surgical units from VAAHS (1 intervention, 1 control) and 4 medical/surgical units from MEDVAMC (2 intervention, 2 control) will be randomly selected to participate in the nurse portion of the project. The nurse manager for each

selected unit will then be approached to obtain approval for the unit to participate. If a nurse manager declines, the next unit on the list will be selected.

For both physicians and nurses, an independent statistician will allocate the teams and units in a concealed fashion, using a computer-generated randomization schema. The physicians and nurses from the intervention groups will receive both independent and group-facilitated mindfulness education, will be encouraged to use a mindfulness mobile app as a practice reminder and additional resource, and instructed to integrate moments of mindfulness with repeated episodes of hand hygiene during the course of caring for patients. The control groups will receive no such education or intervention and will continue as usual.

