There could be a risk of a Hawthorne effect with conducting hand hygiene observations. Three basic, non-technological methods to help avoid or decrease the Hawthorne effect include: 1) letting healthcare workers habituate to unobtrusive and/or frequent observation; 2) using indirect methods to monitor hand hygiene adherence, such as monitoring consumption of hand sanitizer products; and 3) covertly observing hand hygiene adherence.⁸¹ To minimize the risk of Hawthorne effects for this project, research assistants will conduct wash-in period observations within units as a means of habituating physicians and nurses to being observed. Additionally, research assistants will not follow the inpatient teams. Instead, all observations will be done covertly from a randomly chosen location on one of the hospital units each day. As such, we anticipate that research assistants will be able to capture hand hygiene moments for 4-6 patient encounters per observation day. Due to the variable number of patients, team attendance and daily rounding structure, each day we expect to observe approximately 8-24 before room entry and 4-12 after room exit hand hygiene moments, with an additional 2-3 measures of attending hand hygiene duration upon leaving the room. With roughly 10 observational days per attending team (M-F, no weekend or holiday observations) during the intervention period and up to 24 attending teams, we estimate we will collect the following physician data per arm at each site: 1,920-5,670 room entry hand hygiene moments, 960-2,880 room exit hand hygiene moments, and 480-720 measurements of hand hygiene duration.

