5.4 Inclusion/Exclusion Criteria

Aims 1 and 2:

For the nurse portion of the trial, 1 inpatient hospital unit at Ann Arbor VAMC and 2 units at MEDVAMC will be randomized to receive the intervention and an equal number of units at each site will be randomized to receive the control. All nurses on the selected units will be asked to participate in the voluntary study. Inclusion criteria are all nurses on the identified units. There are no exclusion criteria.

For the physician portion of the trial, we will focus on inpatient physician teaching teams, which typically include 1 attending physician, 1 senior resident, and 2-3 intern physicians (Year 1 residents). Inclusion criteria are physicians on inpatient medical teams. Exclusion criteria are medical students, surgical attendings, and physicians on sub-specialty teams. Attending physicians may be on service multiple times per year. Attending physicians will be allowed to participate in multiple months, however, once a physician has been randomized to the intervention arm, they will no longer be eligible to participate in the control arm of the study.

Aim 3:

In this aim we will conduct a qualitative evaluation to better understand the perception of the intervention and assess any barriers or facilitators encountered. The primary subjects will be nurses and physicians that participated in the intervention. Inclusion criteria for this aim is being a nurse or physician that participated in the intervention. There are no exclusion criteria.

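### Physician teams are balanced within hospital, but the adherence model has no site term: a minor loss of efficiency, worth correcting only together with a small-sample correction

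*Protocol*

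**What the plan says.** Protocol section 5.1 (Randomization) allocates physician teams within hospital over 12 months, "with 2 physician teams randomly selected at each site each month for participation (1 intervention, 1 control"). Section 5.2 gives a different count for MEDVAMC (two intervention teams a month, and as many control teams), but it is also balanced within hospital.

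For adherence and duration, section 5.6 plans a Poisson log-link model with robust variance: "Models will account for provider type and level, and will incorporate clustering by physician team (and separately for nursing unit"). Site is not among the terms. It appears only in the power paragraph of the same section, "taking into account clustering of data within site/team/unit (assumed Intraclass Correlation Coefficient=0.4"). No small-sample correction is stated.

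The SAP does not carry the Poisson model. For these outcomes it names only Fisher's "exact test and t-test, as appropriate. Differences in adherence to duration of hand hygiene will be calculated".

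**The concern.** Hospital is a stratum of the allocation. A model that leaves it out discards information the design already holds, and here it does so in the variance. Each team's residual is measured from an arm mean pooled over both hospitals. Teams at the higher-adherence hospital therefore all sit above that mean, and teams at the lower one sit below. The clustered sandwich variance reads this as variation between teams.

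The preliminary data in section 2.0 give reason to expect a gap. Ann Arbor's covert rates were 85% on entry and 81% on exit. MEDVAMC's directly observed rate was 77%, and the investigators expect its covert rate to be slightly lower. At stake is some precision on a primary Aim 1 outcome.

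**Working it through.** **The plan's own power figure.** Section 5.6 states 79.8% power for 334 providers, 60 observations each and ICC 0.4. On the plain reading, the design effect is 1 + 59 × 0.4 = 24.6 and the effective sample is 167 × 60 / 24.6 = 407 per arm. Then 80% v 88% gives 87.7%, so the stated figure is not reproduced. The point here does not depend on it.

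**Inputs.**
- Teams: 2 hospitals × 2 teams × 12 months = 48, or 24 per arm (section 5.1).
- Observations per monthly team: "each day we expect to observe approximately 8-24 before room entry and 4-12 after room exit hand hygiene moments", so 12 to 36 a day. Over 10 days and two attendings ("while attendings rotate approximately every 2 weeks") that is 240 to 720, with midpoint 480.
- Effect: risk ratio 1.10 (section 5.6).
- Hospital rates: 83% (mean of 85% and 81%) v 77%; and 83% v 74%, where 74% is an assumption.
- Team ICC: 0.05 and 0.10 are assumptions. 0.40 is the plan's value, which it does not assign to a single level.

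**The estimate.** With equal team sizes and 1:1 allocation within hospital, the log risk ratio is log(intervention events / control events) with or without site. Only the reported variance differs.

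**Hand check (83% v 77%, ICC 0.05).** Per arm, the team variance relative to the squared mean is [p(1−p)·ICC + p(1−p)(1−ICC)/480] / p².
- Control, p = 0.80: (0.008 + 0.000317) / 0.64 = 0.0130.
- Intervention, p = 0.88: (0.00528 + 0.000209) / 0.7744 = 0.0071.
- With site: √[(0.0130 + 0.0071) / 24] = 0.0289.
- Without site, each arm also carries the squared half-gap, (0.03/0.80)² = 0.0014: √[(0.0201 + 0.0028) / 24] = 0.0309.
- Variance ratio: 0.0201 / 0.0229 = 0.88.

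**Simulation.** Beta-binomial teams, 12 per arm per hospital, fitted by Poisson regression with team-clustered variance. In the cell just worked, the SD of the estimate is 0.0289 under both models. The mean corrected SE is 0.0308 without site and 0.0287 with it. "Corrected" below means a factor K/(K−k) on the variance (K teams, k coefficients) and a t reference on K−k df.

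| Rates | ICC | Variance, site / no site | Power, both corrected: no site → site | Power: no site, plain z → site, corrected | Type I error: no site, plain z |
|---|---|---|---|---|---|
| 83 v 77 | 0.05 | 0.87 | 88 → 90% | 89.1 → 89.9% | 4.7% |
| 83 v 77 | 0.10 | 0.93 | 62 → 65% | 65.6 → 64.8% | 5.4% |
| 83 v 77 | 0.40 | 0.98 | 19 → 19% | 22.4 → 20.0% | 4.8% |
| 83 v 74 | 0.05 | 0.76 | 80 → 87% | 82.9 → 87.1% | 3.7% |
| 83 v 74 | 0.10 | 0.87 | 54 → 60% | 58.6 → 60.6% | 4.3% |
| 83 v 74 | 0.40 | 0.96 | 17 → 18% | 19.6 → 17.7% | 4.6% |

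The two power columns come from separate runs (20,000 and 12,000 per cell) and agree within about one point. Across these cells, type I error with site is about 5.3 to 6.5% by plain z and 3.9 to 4.9% when corrected. With the 72 teams implied by section 5.2, the variance ratios are 0.89, 0.94 and 0.99 at 83 v 77, and 0.80, 0.89 and 0.97 at 83 v 74.

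**The case against.** The strongest reply is that the plan as written loses almost nothing. Section 5.6 states no correction. Read as a plain z-test at 83% v 77%, it is close to nominal, and its mean reported SE is near the true SD (0.0301 v 0.0292 at ICC 0.05; 0.0408 v 0.0404 at ICC 0.10). Replacing it with a corrected site model gains under a point at ICC 0.05 and loses power at 0.10 and 0.40. Adding site alone worsens error control. The only documented ICC, 0.40, makes the gain negligible. The 83% v 77% gap sets covert data against direct observation and is not specific to physicians.

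All of this stands, and it is why the point is minor. But the calibration rests on two departures that happen to offset: an SE inflated by the hospital gap, and a missing small-sample correction. At 83% v 74% and ICC 0.05 they no longer cancel (type I error 3.7%).

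Three stronger readings are tempting, and the documents do not support them:
- **That the omission guarantees a conservative test.** It does not: the no-site z-test gives 4.7 to 5.4% at 83% v 77%.
- **That the power paragraph's mention of site means the model adjusts for it.** That phrase describes the sample size assumption. The model's listed terms do not include site.
- **That many attendings must recur, so that team clustering is invalid.** Section 5.1 expects "up to 24 attending teams, we estimate we will collect the following physician data per arm at each site: 1,920-5,670 room entry" moments, and 24 × 10 days × 8 = 1,920. That gives up to 48 attending slots per arm over both hospitals, against about 35 attendings per arm in section 5.2, which suggests 13 repeats. But 35 counts enrolled attendings, a second attending may decline and still be observed, and 24 is an upper limit. Repeats are allowed ("Attending physicians will be allowed to participate in multiple months, however, once a physician has been randomized to the intervention arm"), but their number is not established.

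**Conclusion.** The point holds as a minor, optional improvement. The adherence model omits the hospital stratum, and if the hospitals differ its reported SE exceeds that of a site-adjusted model. The arm estimate is not biased and its true spread is unchanged.

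Like for like, site is worth about 3 points of power at 83% v 77%, and 6 to 7 at the assumed 83% v 74%, for assumed team ICCs of 0.05 to 0.10. It is worth about 1 point or less at 0.40. Against an uncorrected z-test, a net gain of about 2 to 4 points appears only at 83% v 74% with ICC 0.05 to 0.10.

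Neither MEDVAMC's covert rate nor the team-level ICC is documented. The simulation fits physicians alone without provider-level terms. A model pooling physicians and nurses, which section 5.6 might also mean, was not examined, and nor was duration.

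**What to change.** In the physician adherence model, add site as a fixed effect together with a small-sample correction to the clustered variance, for example K/(K−k) with a t reference on K−k df. The two belong together. Use the same terms for duration, for consistency with the design. Write this model into the SAP.

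The cost is one degree of freedom among 48 teams and slightly wider intervals from the correction. Hospital is known for every observation, so no new data are needed.

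Clustering by attending as well as by team can be an optional sensitivity analysis. It needs an attending code for everyone observed, including those who decline. Section 5.1 plans a study ID on the forms for physician participants, in the context of follow-up, while section 5.2 says the records show only role; these must be reconciled first.

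Two things are not proposed. Terms for each of the 24 hospital-month pairs would leave 48 − 24 − 1 = 23 residual df instead of 48 − 3 = 45, and no month difference is documented. A site term should not be relied on for the six nursing units, where residual df would fall from 4 to 3 and the t critical value would rise from 2.78 to 3.18.
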